## 10.3 Expedited Adverse Event Reporting

### 10.3.1 Rave-CTEP-AERS Integration

The Rave Cancer Therapy Evaluation Program Adverse Event Reporting System (CTEP-AERS) integration enables evaluation of post-baseline AEs entered in Rave to determine whether they require expedited reporting and facilitates entry in CTEP-AERS for those AEs requiring expedited reporting. Sites must initiate all AEs for this study in Medidata Rave.

**Treatment-emergent AEs:** All AEs that occur after baseline are collected in Medidata Rave using the Adverse Event form, which is available for entry at each treatment or reporting period and is used to collect AEs that start during the period or persist from the previous reporting period. CRA will enter AEs that occur prior to the start of treatment on a baseline form that is not included in the Rave-CTEP-AERS integration. AEs that occur prior to enrollment must begin and end on the baseline Adverse Event form and should not be included on the standard Adverse Events form that is available at treatment unless there has been an increase in grade. AEs that occur 30 Days after the Last Administration of the Investigational Agent/Intervention are collected using the Late Adverse Event form.

Prior to sending AEs through the rules evaluation process, site staff should verify the following on the Adverse Event form in Rave:

- The reporting period (course/cycle) is correct, and
- AEs are recorded and complete (no missing fields) and the form is query-free.

The CRA reports AEs in Rave at the time the Investigator learns of the event. If the CRA modifies an AE, it must be re-submitted for rules evaluation.

Upon completion of AE entry in Medidata Rave, the CRA submits the AE for rules evaluation by completing the Expedited Reporting Evaluation form. Both NCI and protocol-specific reporting rules evaluate the AEs submitted for expedited reporting. A report is initiated in CTEP-AERS using information entered in Medidata Rave for AEs that meet reporting requirements. The CRA completes the report by accessing CTEP-AERS via a direct link on the Medidata Rave Expedited Reporting Evaluation form. Contact the CTSU Help Desk at [name] or by email at [[contact]](mailto:[contact]) if you have any issues submitting an expedited report in CTEP-AERS.

In the rare occurrence that Internet connectivity is lost, a 24-hour notification is to be made to CTEP by telephone at [contact]. Once internet connectivity is restored, the

24-hour notification that was phoned in must be entered immediately into CTEP-AERS using the direct link from Medidata Rave.

Additional information about the CTEP-AERS integration is available on the CTSU website:

- Study specific documents: *Protocols > Documents > Protocol Related Documents > Adverse Event Reporting*, and
- Additional resources: *Resources > CTSU Operations Information > User Guides & Help Topics*.

NCI requirements for SAE reporting are available on the CTEP website:

- NCI Guidelines for Investigators: Adverse Event Reporting Requirements is available at [https://ctep.cancer.gov/protocolDevelopment/electronic\\_applications/docs/aeguidelines.pdf](https://ctep.cancer.gov/protocolDevelopment/electronic_applications/docs/aeguidelines.pdf).

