#### 4.3.2 Special Instructions for Patient Enrollment

Pre-registration Step 0 and Registration Step 1 are to be performed at the same time and after patient has completed all elements of the screening and eligibility requirements and is ready to enroll/be randomized.

The Baseline Biopsy is to be conducted after Registration Step 1 is completed and prior to starting the assigned treatment regimen.

This Study will use the ETCTN Specimen Tracking System (STS).

- All biospecimens collected for this trial must be submitted using the ETCTN Specimen

Tracking System (STS) unless otherwise noted.

- The system is accessed through Rave user roles: “Rave CRA” and “Rave CRA (Labadmin)” for data entry at the treating institutions and “Biorepository” for users receiving the specimens for processing and storage at reference labs and the NCI Early-Phase and Experimental Clinical Trials Biospecimen Bank (EET Biobank, formerly known as the ETCTN Biorepository).
- Please refer to the Medidata Account Activation and Study Invitation Acceptance link on the CTSU website in the Data Management section under the Rave Home tab and then under Rave Resource Materials.
- **Important: Failure to complete required fields in STS may result in a delay in sample processing.** Any case reimbursements associated with sample submissions will not be credited if samples requiring STS submission are not logged into STS.

Detailed instructions on use of the STS can be found in Section 5.4.

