## 5. BIOMARKER, CORRELATIVE, AND SPECIAL STUDIES

### 5.1 Summary Table for Specimen Collection

| Time Point   | Specimen   | Send Specimens To:   |
|--|--|--|
| Archival  |  |  |
|  | 
 
Formalin-fixed paraffin-embedded (FFPE) tumor tissue block (preferred) (mandatory)
 
 
If a block is not available, then submit:
 
 
1 H&E stained slide (4 <math>\mu</math>m)
 
15 unstained, 4 micron, positively charged slides, no cover
 
 | [name] Laboratory  |
| Baseline  |  |  |
|  | 
 
3 FFPE tumor tissue blocks (mandatory)
 
2 snap frozen tumor cores (mandatory)
 
  | [name] Laboratory  |
|  | 
 
8.5 mL peripheral blood in FoundationOne Liquid CDx cfDNA tubes (optional) (see Section 11 [Footnote L])
 
   | Foundation Medicine  |
|  | 
 
30 mL peripheral blood in EDTA tubes (mandatory)
 
   | [name] Laboratory  |
|  | 
 
20 mL in Streck cfDNA tube (mandatory)
 
   | EET Biobank  |
| Day 1 of Cycles 1-6, 9 and 12   |  |  |
| 
 
Pre infusion
 
30 minutes after the end of infusion of CDX-1127 (varlilumab), which will be administered after atezolizumab
 
 | 
 
6 mL Peripheral blood in red-top tube processed for serum and frozen (mandatory)
 
   | OSU Comprehensive Cancer Center (OSUCCC) Pharmacoanalytical Shared Resource (PhASR) Laboratory |
| Day 15 of Cycles 1 and 2  |  |  |
| 
 
Pre infusion
 
30 minutes after the end of infusion of CDX-1127 (varlilumab), which will be
 
                                 | 
 
6 mL Peripheral blood in red-top tube processed for serum and frozen (mandatory)
 
   | OSU Comprehensive Cancer Center (OSUCCC) Pharmacoanalytical Shared Resource (PhASR) Laboratory |

|  |   |                     |
|--|---|---------------------|
| administered
after
atezolizumab) |   |                     |
| Cycle 1 Day 21                  |   |                     |

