## 9.5 Reporting and Exclusions

### 9.5.1 Evaluation of Toxicity

All patients will be evaluable for toxicity from the time of their first treatment with cobimetinib, atezolizumab, and CDX-1127 (varlilumab). A baseline measurement and at least 1 laboratory or other safety-related measurement obtained after at least 1 dose of study treatment may be required for inclusion in the analysis of a specific safety parameter (e.g., lab shifts from baseline). A complete list of all AE data will be provided along with an assessment of NCI CTCAE grade and relationship to study drug. The incidence of AEs will be tabulated by subgroups of interest (e.g. grade 3 or higher, organ class, relationship to study drug). For analyses at the individual level, the highest grade and relationship to study drug will be assumed if multiple events have occurred. Toxicity will be tabulated by type and grade and will be summarized with descriptive statistics. Other safety data will be assessed in terms of physical examination, clinical chemistry, hematology, vital signs, and ECGs. Negative binomial regression and Cox proportional hazards models will be used to assess the rate of AE and time to first toxicity, respectively.

While the combination of our proposed three study medications (or similar in-class alternatives) have not been studied in human trials, CDX-1127 (varlilumab) has been shown to be well tolerated in combination with anti-PD1, Nivolumab in patients with advanced solid tumors (NCT02335918). Additionally, the combination of cobimetinib and atezolizumab demonstrated a favorable safety profile at full doses in BTC patients (CTEP 10476). The present study will be continuously monitored for adverse events.

We will incorporate the following safety run-in and stopping rule that will be applied within each treatment group, A and B, respectively: if 2 or more “unacceptable toxicities,” at least possibly attributable to study therapy, are observed among the first 6 patients enrolled in the same treatment arm during their initial treatment cycle, we will pause the accrual in that arm and re-

evaluate safety. Accrual will be limited until the safety has been achieved in the first 6 patients in each arm, respectively.

“Unacceptable toxicities” are defined as the following treatment-related events:

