Adverse Events of Special Interest (AESIs) for this study are related to the biopsy component of the study. These events should be captured in Rave as they occur and should be reported expeditiously according to the table above. Four of these AESIs are not currently part of the CTCAE and must be reported in Rave/CTEP-AERS using the term: Injury, poisoning and

procedural complications - Other, specify. The AESI Terms and Grading Table below (Section 10.3.4.1) lists the AESI terms and their grading. The AESI Reporting Table (Section 10.3.4.2) provides instruction on how to record these events in Rave/CTEP-AERS.

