## 11. STUDY CALENDAR

Informed consent is to be obtained any time prior to conducting research procedures and may be greater than 14 days before Randomization. Baseline timepoint scans, Echocardiogram (or MUGA), Eye Exam, and Pre-Treatment Biopsy are highly recommended to be done within 14 days of randomization but can be done up to a maximum of 28 days prior to randomization, if needed to accommodate scheduling limitations. Screening labs must be done within 14 days of randomization. In the event that the patient's condition is deteriorating, laboratory evaluations should be repeated within 48 hours prior to initiation of the next cycle of therapy. All participants receiving atezolizumab will be assessed for pulmonary signs and symptoms on physical examination as well as imaging throughout the study.

| 1 cycle = 28 days                   | Baseline                            | Cycle 1 |        |        | Cycle 2        |        |        | Cycle 3 and beyond |       |         | Progression/
End of
Treatment s |
|-------------------------------------|-------------------------------------|---------|--------|--------|----------------|--------|--------|--------------------|-------|---------|--|
|                                     |                                     | Day 1   | Day 15 | Day 21 | Day 1          | Day 15 | Day 21 | Day 28             | Day 1 | Day 15  |  |
| Visit window t           | -Day 14
to
Randomi-
zation | +/-2    | +/-2   | +/-5   | +/-2           | +/-2   | +/-5   | +/-2               | +/-2  | +/-5    | +14  |
| Atezolizumab b           |                                     | X       | X      | X      | X              | X      | X      | X                  | X     | X       |  |
| CDX-1127 (vanilimumab) c |                                     | X       | X      | X      | X              | X      | X      | X                  | X     | X       |  |
| Cobimetinib d            |                                     | X-----X |        |        | X-----X        |        |        | X-----X            |       | X-----X |  |
| Informed consent                    | X                                   |         |        |        |                |        |        |                    |       |         |  |

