| N: Baseline scans must be done <4 weeks prior to randomization. Tumor measurement will be performed with contrast CT chest/abdomen/pelvis. Non-contrast CT chest/abdomen/pelvis or CT Chest and MRI Abdomen/pelvis will be performed in subjects with contraindications or intolerance to contrast dye. For the first on-treatment scan, this should be done approximately 8 weeks from the start of treatment (not from the date of the pre-treatment baseline scan). Imaging will be repeated every 8 weeks, irrespective of dosing schedule or treatment delays. For the End of Treatment visit, scans do not need to be repeated if a scan has been performed within 8 weeks. For patients removed from study treatment for reasons other than progression, scans are to continue every 8 weeks until progression. |                                    |                      |         |        |        |         |       |        |                    |        |       |  |        |        |
| O: CA19-9 does not need to be repeated in the event that the screening lab draw show that the patient's tumor does not secrete CA19-9.   |                                    |                      |         |        |        |         |       |        |                    |        |       |  |        |        |
| P: Only for subjects with tumor that in the opinion of the study treatment team is safely accessible for biopsy. See Section 5.5.2 for the order of the tumor cores to be collected. The baseline biopsy is to be done after randomization but before C1D1.  |                                    |                      |         |        |        |         |       |        |                    |        |       |  |        |        |
| Q: Blood collection will be collected at baseline, C1D21, and Week 12 (end of Cycle 3). Pre-treatment baseline EDTA and Streck tube draws should only be drawn on enrolled patients and can be drawn anytime between time of enrollment and prior to start of treatment. These samples must be collected only Monday - Thursday and shipped overnight same day. See Section 5.1 for more details.  |                                    |                      |         |        |        |         |       |        |                    |        |       |  |        |        |

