| AA: Day 0 = time period after randomization up until C1D1 of treatment. Baseline research blood draws (EDTA and Streck tubes) and baseline study tissue biopsies should take place during this period (after patient has completed enrollment and prior to start of therapy).  |                                    |                      |         |        |        |         |       |        |                    |        |       |  |        |        |

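### Complications of the baseline research biopsy arise before first dose, where Section 10.3.1 assigns them a form outside expedited-report evaluation, although Section 10.3.4 requires biopsy AESIs to be reported expeditiously

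*Combined protocol and SAP*

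**What the plan says.** **Timing of the biopsy.** Section 4.3.2: "The Baseline Biopsy is to be conducted after Registration Step 1 is completed and prior to starting the assigned treatment regimen". Footnote P of the Section 11 calendar agrees: "The baseline biopsy is to be done after randomization but before C1D1". Footnote AA defines Day 0 as the interval from randomisation to C1D1 and says "baseline study tissue biopsies should take place during this period". The opening paragraph of Section 11 and footnote A say something different: the pre-treatment biopsy "can be done up to a maximum of 28 days prior to randomization".

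**Status of the biopsy.** Section 5.2 classes both biopsies as research without clinical impact. Section 5.1 marks the baseline tissue as required, but Section 5.5.2 and footnote P limit biopsy to tumours that are amenable or safely accessible.

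**Reporting duty.** Section 10.3.4 makes biopsy-related haemorrhage, nerve injury, organ injury and anaesthesia effects AESIs, together with pneumothorax, pain, wound infection and allergic reaction. It states: "These events should be captured in Rave as they occur and should be reported expeditiously according to the table above".

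**Form.** Section 10.3.1: "CRA will enter AEs that occur prior to the start of treatment on a baseline form that is not included in the Rave-CTEP-AERS integration".

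**Toxicity population.** Section 9.5.1: "All patients will be evaluable for toxicity from the time of their first treatment with cobimetinib, atezolizumab, and CDX-1127 (varlilumab". Section 12.1.1 says the same.

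**The concern.** The biopsy AESI list exists to watch the risk of procedures that bring the patient no clinical benefit. For the first of the two procedures, the AESI section and the form instruction point in different directions. A coordinator who follows Section 10.3.1 to the letter enters a post-biopsy bleed on a form that does not feed the expedited-report rules. A coordinator who follows Section 10.3.4 treats the same bleed as needing expedited handling. Sites may then handle the same event differently.

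There is also an analysis consequence. Toxicity is assessed from first treatment, so a complication on the day of the baseline biopsy predates the period that is summarised. If it stops the patient from starting treatment, the patient is not in the toxicity population at all, and Section 4.4 allows the registration to be cancelled.

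**Working it through.** The plan states no figure on this point, so the check is to follow one event, a bleed on the day of the baseline biopsy, through the text.

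1. **When does it happen?** Under Section 4.3.2 and footnotes P and AA, it happens after randomisation and before C1D1. Under the Section 11 opening paragraph and footnote A, it could happen up to 28 days before randomisation. In both cases it precedes the first dose.

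2. **Which form?** Section 10.3.1 uses three markers: after baseline, before the start of treatment, and before enrolment. It does not say when baseline ends. The sentence on events before the start of treatment covers the bleed directly and assigns the baseline form. If the biopsy was done before randomisation, the further sentence confining pre-enrolment events to the baseline form applies as well. Its exception for a rise in grade would not help with a bleed that is at its worst on the first day.

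3. **What does that form miss?** Section 10.3.1 describes one electronic path. The event goes on the Adverse Event form, the Expedited Reporting Evaluation form is completed, the rules are applied, and a CTEP-AERS report is opened by a direct link. The baseline form is outside this path. The only fallback given is a telephone call when the internet is down, and that call must later be entered through the same link.

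4. **What does the AESI rule require?** Section 10.3.4 asks for entry as events occur and expedited reporting according to the table above it. Sections 10.3.4.1 and 10.3.4.2 give grades and terms. None of them exempts the baseline biopsy or offers it another route.

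5. **Does that table cover the event?** The heading of the Section 10.3.3 table frames it by time since the last administration of agent, up to 30 days, and its footnote deals with later events. No start is defined, so an event before any dose is not clearly inside it.

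6. **Is it summarised?** Sections 9.5.1 and 12.1.1 start at first treatment. The run-in rule in Section 9.5.1 counts only the initial treatment cycle.

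**Scale.** Inputs: 64 evaluable patients (Section 9.2) and two biopsies each, at baseline and C1D21 (Section 5.5.2). Planned procedures if every one of the 64 has both: 64 × 2 = 128. Baseline share: 64 / 128 = 50%. This is an upper limit for treated patients, because biopsy depends on safe access. It counts procedures, not complications. With equal numbers biopsied at each time point and complication rates p1 (baseline) and p2 (C1D21), the baseline share of complications is p1 / (p1 + p2). The documents give neither rate, so that share could lie anywhere from 0 to 1.

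**The case against.** The strongest reply is that the duty to report is intact. Section 10.3.3 requires investigators to report any serious adverse event to the sponsor immediately, related or not. Section 10.4 requires all adverse events in routine data, and Section 10.3.4 is specific to biopsies while Section 10.3.1 is general. The data are also kept. Section 10.3.1 has every event initiated in Rave, Section 13.2.2 has those data reviewed as they arrive, Section 13.1 gives the Protocol Principal Investigator and the statistician access at all times, and Section 9.5.1 promises a full listing of adverse events. Section 10.3.1 is itself loose: it confines to the baseline form only events before enrolment, so a reader could place a post-enrolment bleed on the standard form. It also points to study-specific reporting documents and NCI guidelines that are not part of the text reviewed.

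Most of this stands, and it limits the point. It does not remove the conflict. Section 10.3.3 requires electronic submission, and the only electronic route described is the one the baseline form lies outside. Routine capture is not the expedited reporting that Section 10.3.4 asks for. A listing gives no denominator of biopsied patients.

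It may also be said that starting drug toxicity at first treatment is an ordinary safety definition. That is right, and it is not an error in itself. The gap is that no other summary picks up procedure harm before dosing.

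**Conclusion.** The conflict is real and lies in the current text. Baseline-biopsy complications that arise before first dose are assigned a form that bypasses expedited-report evaluation, under a reporting table that does not clearly cover them, and they fall outside the toxicity summary. Up to one of two planned biopsies per patient is affected. C1D21 biopsies, and delayed complications that first appear after C1D1, reach the integrated form.

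A reader might infer three stronger things, and the documents support none of them:

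- **That expedited reporting of these events is lost or forbidden.** Sections 10.3.3, 10.3.4 and 10.4 keep the duty. What is bypassed is the prescribed route.
- **That the biopsy complication count is understated by about half.** This needs equal complication rates at both time points, both biopsies in every patient, and every baseline event dropped. The first is not given, the second is contradicted by the access limit, and the third by recording in Rave.
- **That the worst cases disappear or that the monitoring board is misled.** Section 9.6 does not say what the board's reports contain, and the events remain in the database.

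The conclusion assumes that the start-of-treatment sentence in Section 10.3.1 means what it says, and that no outside reporting guide overrides it.

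**What to change.** 1. **Section 10.3.1:** state that the AESIs listed in Section 10.3.4.1, when they follow the baseline biopsy, go on the integrated Adverse Event form and through expedited-report evaluation even if no dose has been given.
2. **Section 10.3.3:** start the reporting period for these events at the biopsy.
3. **Section 9.5.1:** tabulate biopsy AESIs by time point, with all patients who underwent that biopsy as the denominator, treated or not. Keep the treatment-based population for drug toxicity.
4. **Section 11:** reconcile the biopsy window in the opening paragraph and footnote A with Section 4.3.2 and footnotes P and AA.

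The cost is a few sentences of protocol text, a small form-routing change in Rave and one extra safety table. It needs no additional patients or procedures.

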#### **10.3.2 Distribution of Adverse Event Reports**

CTEP-AERS is programmed for automatic electronic distribution of reports to the following individuals: Principal Investigator and Adverse Event Coordinator(s) (if applicable) of the Corresponding Organization or Lead Organization, the local treating physician, and the Reporter and Submitter. CTEP-AERS provides a copy feature for other e-mail recipients.

